3.1.3 Dose-Limiting Toxicity Assessment Window

For all patients enrolled in the vemurafenib and cobimetinib combination cohorts, DLTs will be assessed during a DLT assessment window of 28 days in Cycle 1. The 28-day DLT window will not apply for patients treated with single-agent cobimetinib.

Dose reductions are not allowed during the DLT window for a patient to count in dose-escalation decisions.

Patients who discontinue study treatment or miss 3 or more total days of either vemurafenib or cobimetinib prior to completing the DLT assessment window for any reason other than DLT will be replaced.

3.1.4 Rules for Dose-Escalation and Potential Dose De-Escalation; Changes in Dose Scheduling following Dose-Limiting Toxicity

Dose escalation will occur in accordance with the rules listed below. Intra-cohort dose escalation is not allowed.

- A minimum of 3 patients will be initially enrolled per cohort
- If 1 of the first 3 patients enrolled in a given cohort experiences a DLT, at least 3 additional patients will be enrolled in that cohort.
- If fewer than one-third of evaluable patients in a given cohort experiences a DLT (e.g., DLTs in fewer than 1 of 3 or 2 of 6 patients), escalation will proceed to the next higher dose cohort.
- If a DLT is observed in one-third or more of patients (e.g., 2 or more of up to 6 patients), the dose combination at which this occurs will be considered intolerable, and the MTD will have been exceeded.

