3.1.5 Definition of Dose-Limiting Toxicity

Adverse events will be graded according to the National Cancer Institute Common Terminology Criteria for Adverse Events, Version 4.0 (NCI CTCAE v4.0). A copy of this grading scale will be provided to the study sites upon request or can be accessed at http://ctep.cancer.gov/protocolDevelopment/electronic_applications/ctc.htm

DLT definitions reflect the known and expected toxicities of vemurafenib and cobimetinib.

A DLT definition is defined as one of the following toxicities occurring during the DLT assessment window and considered by the investigator to be related to study treatment (per guidance in Section 7).

- Grade ≥ 3 non-hematologic, non-hepatic organ toxicity, EXCLUDING the following:
 - a) Grade 3 nausea or vomiting that resolves to Grade ≤ 1 within 7 days of appropriate supportive therapy
 - b) Grade 3 diarrhea that resolves to Grade ≤ 1 within 7 days with appropriate supportive therapy
 - c) Grade 3 rash that resolves to Grade ≤ 2 within 7 days with appropriate supportive therapy
 - d) Grade 3 photosensitivity that resolves to Grade ≤ 2 within 7 days with appropriate supportive therapy
 - e) Grade 3 cuSCC that is subsequently resected
 - f) Grade ≥ 3 fatigue that resolves to Grade ≤ 2 within 7 days
 - g) Grade ≥ 3 hyperuricemia that resolves to Grade ≤ 2 within 7 days
 - h) Grade 3 fever
 - i) Grade 3 or 4 elevation of serum CPK levels, which is asymptomatic (i.e., not accompanied by signs, symptoms, or other laboratory abnormalities associated with rhabdomyolysis or myocardial injury), deemed by the investigator to be clinically insignificant and that returns to Grade ≤ 2 within 14 days of cobimetinib treatment interruption.
- Grade ≥ 3 febrile neutropenia
- Grade ≥ 4 neutropenia (ANC $< 500/\mu\text{l}$)
- Grade ≥ 4 thrombocytopenia
- Grade ≥ 4 anemia
- Grade ≥ 3 total bilirubin, hepatic transaminase (ALT or AST), ALP, with the following exceptions:
 - Patients with Grade 2 hepatic transaminase or ALP elevation at baseline as a result of metastases; for these patients, hepatic transaminase or ALP elevation ≥ 10 x upper limits of normal (ULN) will be considered a DLT.

All DLTs will be reported by telephone to the Medical Monitor within 24 hours.

3.1.6 Dosing beyond Cycle 1

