4.7 Replacement Policy (Ensuring Adequate Numbers of Evaluable Patients)

4.7.1 For Patients

No patient prematurely discontinued from the study for any reason, after having completed the first cycle (first 28 days on the study), will be replaced. Patients who discontinue study treatment or have missed 3 or more days in total of either study drug in the first 28-day cycle for reasons other than a DLT will be replaced.

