Table 12 Vemurafenib and Cobimetinib Dose Modification Guidelines (Cont.)

Adverse Event	Action

B) Photosensitivity: Grade ≥ 3
	
a) In cases of Grade 2 photosensitivity, treatment with vemurafenib and cobimetinib may be continued for up to 1 week with the initiation of supportive measures. If the photosensitivity does not resolve to Grade ≤ 1 during this time or if the photosensitivity worsens to Grade ≥ 3, then both vemurafenib and cobimetinib treatment must be interrupted until the photosensitivity resolves to a Grade ≤ 1. If this occurs within 28 days, treatment may be re-initiated with vemurafenib dose reduced by one level (e.g., 720 to 480 mg).
 
b) If the photosensitivity does not resolve to Grade ≤ 1 by 28 days, then the therapy with vemurafenib and cobimetinib should be discontinued.
 
c) If the photosensitivity recurs to Grade ≥ 3 with vemurafenib and cobimetinib, re-initiation despite prophylactic measures and the dose reduction of vemurafenib, then both agents should be held until the photosensitivity resolves to Grade ≤ 1 or less. Cobimetinib should be dose reduced by one level when treatment is re-initiated (e.g., 80 to 60 mg on a 14/14 day schedule; from 60 to 40 mg on a 21/7 or a continuous schedule). The dose of vemurafenib should be maintained at the previously reduced dose.
 
d) If photosensitivity recurs a second time to Grade ≥ 3 despite prophylactic measures and the aforementioned dose reductions of vemurafenib and cobimetinib, either one or both study treatments may resume if in the investigator’s judgement, the benefit-risk of treatment remains favorable.

C) New skin lesion, suggestive of SCC; SCC is considered a Grade 3 event in NCI CTCAE v4.0
	
a) Follow SCC Risk Management Plan detailed in protocol (Section 5.3.4.6)
 
b) Interrupt vemurafenib and cobimetinib for 48 hours before and after excisional biopsy. This period of interruption may be altered based upon experience in this study.
 
c) If lesion is diagnosed as SCC, treatment may be re-instituted with vemurafenib and cobimetinib at pre-event dose levels after the lesion is excised. If the lesion is not excised, vemurafenib treatment may be resumed if in the investigator’s judgement, the benefit-risk of treatment remains favorable.
 
d) If the lesion is not an SCC, then treatment with vemurafenib and cobimetinib may be restarted at the most recent dose level.

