
E) Diarrhea (Grade ≥ 3)
	
a) No change in vemurafenib and cobimetinib dosing will be implemented for Grade 2 diarrhea; patients should receive maximal supportive care per institutional guidelines.
 
b) If Grade ≥ 3 diarrhea occurs despite supportive care, then both drugs should be held until the diarrhea has improved to Grade ≤ 1. If this occurs within 28 days, vemurafenib and cobimetinib may be restarted with cobimetinib dose reduced by one level (e.g., 80 to 60 mg on a 14/14 day schedule; 60 to 40 mg on a 21/7 or a continuous schedule).
 
c) If the diarrhea is not completely resolved by 28 days, then either one or both study treatments may resume if in the investigator's judgement, the benefit-risk of treatment remains favorable.
 
d) If Grade ≥ 3 diarrhea recurs despite supportive care and cobimetinib dose reduction, vemurafenib and cobimetinib should be held until the diarrhea resolves to Grade < 1. If this occurs within 28 days, then therapy may be re-initiated with vemurafenib dose reduced by one level (e.g., 720 to 480 mg). The cobimetinib dose may be maintained at the previously reduced dose.
 
e) If the diarrhea recurs at Grade ≥ 3 despite supportive care and dose reductions in both drugs, then either one or both study treatments may resume if in the investigator's judgement, the benefit-risk of treatment remains favorable.

Table 12 Vemurafenib and Cobimetinib Dose Modification Guidelines (Cont.)

Adverse Event	Action
F) Rhabdomyolysis or symptomatic CPK elevations	
a) Interrupt cobimetinib treatment. If severity is improved by at least on grade within 4 weeks, restart cobimetinib at a dose reduced by 20 mg, if clinically indicated. Vemurafenib dosing can be continued when cobimetinib treatment is modified, if clinically indicated.
 
b) If rhabdomyolysis or symptomatic CPK elevation do not improve within 4 weeks, permanently discontinue cobimetinib treatment.

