8.2.6 Determination of Maximal Tolerated Dose

Patients who withdraw from the study or who miss more than the allowed number of vemurafenib or cobimetinib doses prior to Cycle 1, Day 28 for reasons other than a DLT will be considered unevaluable for DLTs and will not be included in the determination of the MTD of the vemurafenib and cobimetinib combination. The MTD of the vemurafenib and cobimetinib combination will be determined according to the rules described in Section 3.1.4. In the event dose escalation does not continue until the MTD can be determined (e.g., because of PK futility), the MTD will be reported as “undetermined.”

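### The Cycle 1 evaluability rules can drop patients from the DLT fraction because of study-drug toxicity, nothing displays how many, and the sections that define evaluability disagree

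*Combined protocol and SAP*

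**What the plan says.** **Replacement.** Section 3.1.3 covers "Patients who discontinue study treatment or miss 3 or more total days of either vemurafenib or cobimetinib prior to completing the DLT assessment window". It replaces them whatever the cause, with a DLT as the only exception. Section 4.7.1 repeats the 3-day limit for the first cycle, with the same single exception. Under Section 8.2.6, patients who withdraw, or who exceed the permitted number of missed doses, without a DLT "will be considered unevaluable for DLTs and will not be included in the determination of the MTD". That section does not state the permitted number.

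**Dose reduction.** Section 3.1.3 also leaves a patient whose dose is reduced in the window out of escalation decisions. That sentence carries no DLT exception.

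**Events that are not DLTs.** Section 3.1.5 excludes, among others, "Grade 3 cuSCC that is subsequently resected" and Grade 3 diarrhea that falls to Grade 1 or less within 7 days with supportive therapy.

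**Holds in the same window.** Section 6.1.1 applies Table 12 during the DLT window as well as after it. Row C reads "Interrupt vemurafenib and cobimetinib for 48 hours before and after excisional biopsy", and adds that this period may be changed with experience. Row E reads "If Grade ≥ 3 diarrhea occurs despite supportive care, then both drugs should be held until the diarrhea has improved to Grade ≤ 1"; a restart within 28 days is at a reduced cobimetinib dose.

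**Other definitions.** Section 8.2.3 makes a dose-escalation patient evaluable on completing Day 28, or on a DLT with withdrawal. Section 8.3 replaces only patients who withdraw.

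**The concern.** The 3+3 rule in Section 3.1.4 works on DLTs among evaluable patients. If a patient can become unevaluable because of a related toxicity, whether that patient enters the fraction depends on the outcome being studied. The replacement patient is then someone who had a DLT or who took nearly all doses.

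The primary objective is the safety and tolerability of the combination, including the DLTs that determine the MTD and a dose and schedule for later phases. A reader of a result such as 0/3 or 1/6 cannot tell how many further patients at that dose were set aside, or whether toxicity was the cause. Because the sections disagree, two analysts could also count the same patient differently.

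**Working it through.** **1. The same patient under each section.**

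| Cycle 1 course | 3.1.5 | Table 12 | 3.1.3 / 8.2.6 | 8.2.3 |
|---|---|---|---|---|
| Grade 3 cuSCC, resected, pre-event dose resumed, Day 28 reached | Not a DLT | Both drugs off 48 h + 48 h = 96 h, about 4 days | Replaced, not in the MTD count | Evaluable |
| Grade 3 diarrhea, Grade 1 or less after 3 to 7 days, Day 28 reached | Not a DLT | Both drugs off 3 to 7 days; restart at a reduced cobimetinib dose | Replaced, and uncounted if reduced in the window | Evaluable |

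Vemurafenib is dosed on all 28 days (Section 3.1.1), so a hold of about 4 days passes the 3-day limit on every cobimetinib schedule. Grade 3 rash and photosensitivity that resolve within the limits in 3.1.5 can follow the same route: Table 12 holds one or both drugs and then reduces a dose.

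**2. The plan's own figures.** With DLT probability p, the chance of adding three patients is 3p(1−p)², and the chance of clearing the dose is

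C(p) = (1−p)³ + 3p(1−p)² × (1−p)³.

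At p = 0.10, 0.20, 0.33, 0.40, 0.50 and 0.60, C(p) = 0.906, 0.709, 0.434, 0.309, 0.172 and 0.082. Table 13 gives 0.91, 0.71, 0.43, 0.31, 0.17 and 0.08, so it reproduces, and so does its column for adding three patients. The table treats every patient as evaluable and does not model replacement.

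**3. Adding unevaluable patients.** Let d be the probability of a DLT. Let u be the probability of related non-DLT toxicity that leads to 3 or more missed days or to stopping in Cycle 1. The two are taken as mutually exclusive. **u is an assumption; the documents do not give it.** Patients uncounted only because of a dose reduction would add to u.

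- Plan's rule (replace): p = d/(1−u).
- Bounding case (every such patient an event): p = d + u.
- All kept as evaluable non-DLTs: p = d.

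For d = 0.10:

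| u | d/(1−u) | Plan's rule | d + u | All as events | All as non-DLTs |
|---|---|---|---|---|---|
| 0.10 | 0.111 | 0.89 | 0.20 | 0.71 | 0.91 |
| 0.20 | 0.125 | 0.86 | 0.30 | 0.49 | 0.91 |
| 0.30 | 0.143 | 0.83 | 0.40 | 0.31 | 0.91 |

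Example at u = 0.20: p = 0.10/0.80 = 0.125, and C = 0.875³ + 3 × 0.125 × 0.875⁵ = 0.670 + 0.192 = 0.862.

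For other DLT rates, in the order plan's rule, all as events, all as non-DLTs: d = 0.05 with u = 0.30 gives 0.95, 0.40 and 0.97; d = 0.20 with u = 0.20 gives 0.60, 0.31 and 0.71.

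**4. How often it would arise.** The chance that at least one of the first three patients is replaced, 1−(1−u)³, is 0.27, 0.49 and 0.66 for u = 0.10, 0.20 and 0.30. Expected enrolment for six evaluable patients, 6/(1−u), is 6.7, 7.5 and 8.6. At u = 0.20 about 1.5 patients are set aside on average. With one DLT, the formal fraction is then 1/6 = 0.17, and with those patients added to both parts it is 2.5/7.5 = 0.33.

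**The case against.** A minimum-exposure criterion with replacement is a legitimate design choice: it keeps under-exposed patients from counting as evidence that a dose is tolerated.

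The fraction is also not the only evidence. Under Section 3.1.4 a committee that includes a statistician reviews adverse events and dose logs before deciding on escalation, the sponsor may halt or modify escalation, and the recommended dose draws on all treated patients in both stages. Section 3.2 allows expansion accrual to be halted for toxicity. Sections 8.2.3 and 8.2.4 use the treated population and present interruptions with reasons. All of this stands. It limits the effect, but no section requires a count, by cohort, of patients set aside for toxicity.

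The evidence on size is weak, and that also stands. The documents put cuSCC at about 20% of vemurafenib recipients, mostly within 16 weeks, and say the combination may lower it. The 6.5% for Grade 3 or 4 diarrhea is not a Cycle 1 figure and does not require 3 missed days. The statement that about half of vemurafenib patients needed an interruption or reduction is likewise not a Cycle 1 rate. Row C allows its hold to be changed, although as written it exceeds the limit.

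A reader might infer three stronger claims that the documents do not support:

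- **That tolerability is judged only on patients who could stay on drug.** Patients whose missed doses are due to a DLT are exempt from replacement, and the wider review uses everyone treated.
- **That a toxicity listed as a non-DLT makes a patient unevaluable in itself.** Only missed days, stopping or a dose reduction does. Asymptomatic Grade 3 CPK elevation needs no hold, Grade 3 fever has no row of its own in Table 12, and events that outlast the limits in 3.1.5 become DLTs and count.
- **That keeping these patients as non-DLTs would tighten the rule.** It would loosen it: 0.91 against 0.89 to 0.83.

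**Conclusion.** The point holds for the formal DLT/evaluable fraction. Sections 3.1.3, 4.7.1 and 8.2.6 make no distinction between study-drug toxicity and other causes. Together with 3.1.5 and Table 12, they produce patients who are neither DLTs nor evaluable. Sections 8.2.3 and 8.3 give a different answer for some of the same patients.

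The inconsistency follows from the text and needs no assumption. The size does: at d = 0.10 and u of 0.10 to 0.30, the distance from the plan's clearance probability to the bounding case is 0.18 at the low end (0.89 − 0.71) and 0.52 at the high end (0.83 − 0.31, rounded). Those are outer limits, because the bounding case counts every such patient as an event, which 3.1.5 does not do. They do not estimate error in this trial's MTD. What is established is that the exclusion can depend on toxicity and that the planned tables would not show how often it did.

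**What to change.** 1. **Show the patients.** At each cohort review and in the MTD table, give the number of replaced or otherwise uncounted patients by cohort and reason (related toxicity or other). Beside DLTs/evaluable, give a sensitivity fraction: (DLTs + patients unevaluable because of related toxicity) / (evaluable + the same patients).
2. **Reconcile the text.** Align Section 3.1.3 (including its dose-reduction sentence), 3.1.5, 4.7.1, 8.2.3, 8.2.6, 8.3 and Table 12 so that each patient has one evaluability status, and state the missed-dose limit in 8.2.6. The choice of clinical rule is the sponsor's; no change to the DLT list or to the dosing guidance is proposed here.

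Section 18 says a clinical study report has already been written. Where escalation is complete, item 1 becomes a reported sensitivity analysis.

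The cost is small: adverse events and dose logs are already reviewed, and interruptions are already summarised with reasons. It comes to one extra table column and some wording, and some cohorts may show a less favourable tolerability figure.

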3.1.5 Definition of Dose-Limiting Toxicity

Adverse events will be graded according to the National Cancer Institute Common Terminology Criteria for Adverse Events, Version 4.0 (NCI CTCAE v4.0). A copy of this grading scale will be provided to the study sites upon request or can be accessed at http://ctep.cancer.gov/protocolDevelopment/electronic_applications/ctc.htm

DLT definitions reflect the known and expected toxicities of vemurafenib and cobimetinib.

A DLT definition is defined as one of the following toxicities occurring during the DLT assessment window and considered by the investigator to be related to study treatment (per guidance in Section 7).

- Grade ≥ 3 non-hematologic, non-hepatic organ toxicity, EXCLUDING the following:
 - a) Grade 3 nausea or vomiting that resolves to Grade ≤ 1 within 7 days of appropriate supportive therapy
 - b) Grade 3 diarrhea that resolves to Grade ≤ 1 within 7 days with appropriate supportive therapy
 - c) Grade 3 rash that resolves to Grade ≤ 2 within 7 days with appropriate supportive therapy
 - d) Grade 3 photosensitivity that resolves to Grade ≤ 2 within 7 days with appropriate supportive therapy
 - e) Grade 3 cuSCC that is subsequently resected
 - f) Grade ≥ 3 fatigue that resolves to Grade ≤ 2 within 7 days
 - g) Grade ≥ 3 hyperuricemia that resolves to Grade ≤ 2 within 7 days
 - h) Grade 3 fever
 - i) Grade 3 or 4 elevation of serum CPK levels, which is asymptomatic (i.e., not accompanied by signs, symptoms, or other laboratory abnormalities associated with rhabdomyolysis or myocardial injury), deemed by the investigator to be clinically insignificant and that returns to Grade ≤ 2 within 14 days of cobimetinib treatment interruption.
- Grade ≥ 3 febrile neutropenia
- Grade ≥ 4 neutropenia (ANC $< 500/\mu\text{l}$)
- Grade ≥ 4 thrombocytopenia
- Grade ≥ 4 anemia
- Grade ≥ 3 total bilirubin, hepatic transaminase (ALT or AST), ALP, with the following exceptions:
 - Patients with Grade 2 hepatic transaminase or ALP elevation at baseline as a result of metastases; for these patients, hepatic transaminase or ALP elevation ≥ 10 x upper limits of normal (ULN) will be considered a DLT.

All DLTs will be reported by telephone to the Medical Monitor within 24 hours.

3.1.6 Dosing beyond Cycle 1

Treatment will continue until disease progression, unacceptable toxicity, or any other discontinuation criterion is met (Section 4.5). There may be circumstances in which one of the study drugs is discontinued (e.g., as outlined in dose modification, Section 6.1). In the case of permanent cobimetinib discontinuation, patients previously treated with vemurafenib should come off the study. In the case of permanent vemurafenib discontinuation, it will be possible for the patient to continue treatment with single-agent cobimetinib until disease progression, unacceptable toxicity, or any other discontinuation criterion is met (see Section 4.5). In patients without prior treatment for locally advanced and unresectable or metastatic melanoma, permanent discontinuation of either drug while continuing the other will not be grounds for study discontinuation.

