1.2.4.4 Liver Injury

An analysis of liver-related adverse events reported with vemurafenib use showed that 63 cases (out of estimated exposure of approximately 20,000 patients) of medically confirmed serious adverse events were consistent with drug-induced liver injury based on clinical chemistry criteria from the Drug-Induced Liver Injury Expert Working Group

[20]. Of the 63 cases, 2 were assessed as severe, both reported as hepatic failure. There were no reported deaths among the 63 cases of liver injury; the outcomes of the 2 cases of severe liver injury were reported as completely resolved with vemurafenib discontinuation. The median time to onset of the adverse events was 44 days after initial dose. The median ALT to ALP ratio was calculated as 1.5, which suggested a trend towards cholestatic pattern of liver injury. The analysis did not reveal any risk factors or populations at risk.

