1.3.7.5 Liver Laboratory Abnormalities

Liver laboratory test abnormalities, including elevations in AST and/or ALT, have been reported as adverse events and serious adverse events in patients treated with vemurafenib+cobimetinib. In the Phase III study (GO28141), liver laboratory test abnormalities reported as Grade ≥ 3 adverse events occurred more frequently in patients treated with vemurafenib+cobimetinib than vemurafenib+placebo (20.5% vs. 15.1%). Liver laboratory test abnormalities reported as Grade ≥ 3 adverse events at frequencies $\geq 2\%$ higher in patients treated with vemurafenib+cobimetinib than vemurafenib+placebo included increased ALT (11.4% vs. 6.3%), increased AST (8.3% vs. 2.1%), and increased ALP (4.3% vs. 1.7%).

In Study MEK4592g, there were no reported adverse events or serious adverse events for clinically significant Grade 4 elevations in liver laboratory tests, and no patient experienced findings suggestive of drug-induced liver injury or liver failure.

Generally, elevations in liver laboratory tests were managed effectively with dose modification guidelines. In both study arms of GO28141, the majority of Grade ≥ 3 liver laboratory test abnormalities resolved.

Refer to Section [6.1](#) for management of liver laboratory abnormalities.

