Table 12 Vemurafenib and Cobimetinib Dose Modification Guidelines (Cont.)

Adverse Event	Action
K) Other Grade 4, non-hematologic adverse events related to study drug	
a) Interrupt dosing of vemurafenib and cobimetinib.
 
b) If adverse event resolves to Grade ≤ 1 within 28 days, then (at investigator discretion) restart dosing of vemurafenib and cobimetinib. Both should be decreased by one dose level of the pre-event dose (e.g., 960 to 720 mg for vemurafenib; 80 to 60 mg for cobimetinib on a 14/14 day schedule).
 
c) If the adverse event does not resolve to Grade ≤ 1 within 28 days, discontinue study treatment.
 
d) If the adverse event recurs after 1 dose reduction, either one or both study treatments may resume if in the investigator’s judgement, the benefit-risk of treatment remains favorable.

bid=twice daily; LFT=liver function test; QTc=corrected QT interval; RVO=retinal vein occlusion; SCC=squamous cell carcinoma.

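### Under Section 3.1.5 a related Grade ≥3 clinical liver event with no qualifying laboratory value is not a DLT, and the patient can be replaced

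*Combined protocol and SAP*

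**What the plan says.** Section 3.1.5 requires a DLT to be one of a listed set of toxicities, to occur in the 28-day window and to be judged related. The list has no catch-all item. Two items bear on the liver:

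- The general organ-toxicity item is "Grade ≥ 3 non-hematologic, non-hepatic organ toxicity, EXCLUDING the following", followed by named exclusions.
- The hepatic item is "Grade ≥ 3 total bilirubin, hepatic transaminase (ALT or AST), ALP, with the following exceptions". The exception covers patients whose transaminases or ALP are already Grade 2 at baseline because of metastases; for them those tests count only from 10 x ULN.

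Three other rules depend on whether an event is a DLT. Section 3.1.3 replaces patients who discontinue or who "miss 3 or more total days of either vemurafenib or cobimetinib prior to completing the DLT assessment window for any reason other than DLT". Section 4.7.1 says the same of those who "have missed 3 or more days in total of either study drug in the first 28-day cycle for reasons other than a DLT". Under Section 8.2.6, patients who withdraw or miss too many doses for a non-DLT reason "will be considered unevaluable for DLTs and will not be included in the determination of the MTD".

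For related Grade 4 non-hematologic events without a row of their own, Table 12 row K (Section 6.1.1) instructs: "Interrupt dosing of vemurafenib and cobimetinib".

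**The concern.** The first item removes hepatic organ toxicity, and the hepatic item brings back only bilirubin, ALT/AST and ALP values. A related Grade ≥3 clinical liver event without a qualifying value falls between them. The gap is somewhat wider in patients with Grade 2 baseline elevation from metastases, because their transaminase and ALP threshold is raised and no clinical criterion stands behind it.

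The 3+3 rule in Section 3.1.4 counts only DLTs. A patient with such an event either stays in the denominator as a non-DLT or, after three missed days, drops out and is replaced. Both routes lower the counted DLT rate. In a cohort of six with one listed DLT and one such liver event, the true count is 2/6 and the MTD has been exceeded. The written rule can score it 1/6 and clear the dose.

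**Working it through.** **1. Does any other text bring the event back in?** Section 8.2.1 bases the recommended dose on DLTs in the first 28 days. Section 8.2.3 makes patients evaluable if they complete the window, or have a DLT in it and are withdrawn. Neither widens the definition in Section 3.1.5, and no other section does.

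**2. The plan's own figure.** Under the 3+3 rule with true DLT rate p, a dose is called tolerated with 0/3, or with 1/3 followed by 0/3:

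P(tolerated) = (1−p)³ + 3p(1−p)⁵

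At p = 0.33: 0.67³ + 3 × 0.33 × 0.67⁵ = 0.3008 + 0.1337 = 0.4344 (unrounded sum). Table 13 prints 0.43. Its other rows also reproduce: 0.906, 0.709, 0.309, 0.172 and 0.082 at p = 0.10, 0.20, 0.40, 0.50 and 0.60.

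**3. Size of the gap.** Let p be the total rate of limiting events and h the part that is clinical-hepatic without a qualifying laboratory value.

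- Patient replaced: counted rate = (p−h)/(1−h).
- Patient kept as a non-DLT (fewer than three days missed): counted rate = p−h.
- Chance that at least one of n escalation patients is affected: 1−(1−h)ⁿ. Section 8.3 expects n of 30 to 60.

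**4. The value of h is an assumption.** The documents give none for the combination. The nearest figure is in Section 1.2.4.4, on vemurafenib safety reports from about 20,000 exposed patients: "Of the 63 cases, 2 were assessed as severe, both reported as hepatic failure". That is 2/20,000 = 0.01%. Those cases were identified by chemistry criteria and the median onset was 44 days, beyond the 28-day window, so this is a low anchor and not an estimate. The single-agent cobimetinib study MEK4592g cannot supply a rate either. Section 1.3.6.1 reports one Grade 4 hepatic encephalopathy, counted there as a DLT, among 115 treated patients, but gives no laboratory values for it. Section 1.3.7.5 says of the same study that "no patient experienced findings suggestive of drug-induced liver injury or liver failure". I use h from 0.01% to 2%.

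**5. Results at p = 0.33.**

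| Assumed h | Counted rate, replaced | P(tolerated), replaced | P(tolerated), kept as non-DLT | ≥1 affected in 30 | ≥1 affected in 60 |
|---|---|---|---|---|---|
| 0 | 0.3300 | 0.4344 | 0.4344 | – | – |
| 0.01% | 0.3299 | 0.4346 | 0.4346 | 0.3% | 0.6% |
| 0.5% | 0.3266 | 0.4410 | 0.4442 | 14.0% | 26.0% |
| 2% | 0.3163 | 0.4613 | 0.4740 | 45.5% | 70.2% |

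Example: h = 2% with replacement gives (0.33−0.02)/0.98 = 0.3163, and P(tolerated) rises by 0.4613−0.4344 = 0.0269. At p = 0.40 with replacement, 0.3093 becomes 0.3094, 0.3142 and 0.3296 for the same three values of h.

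**6. What a changed decision needs.** To turn a true 2/6 into 1/6 by replacement, there must be such an event, at least three missed days, another DLT in the same cohort, a replacement patient without a DLT, and a committee that still clears the dose.

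**The case against.** The strongest reply is that the event is hypothetical. It needs a severe clinical liver event in Cycle 1 with no qualifying bilirubin, transaminase or ALP value, although chemistry is drawn repeatedly in that cycle (Table 9). Many severe liver events would meet a laboratory threshold, and encephalopathy could be scored as neurological under the general item. Section 3.1.5 says its definitions follow the expected toxicities, and the documented hepatic signal is mainly laboratory elevation. At the only documented anchor the shift is 0.0001, invisible at Table 13's two decimals; the larger figures need h 50 to 200 times that anchor.

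Safeguards also exist. Entry criteria limit liver tests, albumin and INR (Section 4.2) and exclude significant liver disease (Section 4.3). Grade 3 and 4 events in the window are expedited (Section 3.10.3), as are potential Hy's-law cases (Section 7.1.1.5). The committee reviews adverse events and dose logs, and the sponsor may halt escalation (Section 3.1.4). A DSMB reviewed safety about every three months (Section 10), and expansion accrual stops if toxicity suggests the MTD is exceeded (Section 3.2). The recommended Phase II dose draws on all treated patients (Section 3.1.4), so a replaced patient still informs it. Finally, a clinical study report exists (Section 18), so rewording may change nothing prospectively.

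Rarity and the limited prospective effect stand. The safeguards reduce the practical risk, but none alters the DLT count, the replacement rule or the MTD definition. Nor is the event type foreign to the programme: the encephalopathy in MEK4592g was a DLT in its own study, and Section 3.10.2.2 names severe hepatotoxicity as a potential cobimetinib risk. Whether such an event counts should not depend on coding it as neurological.

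**Conclusion.** The concern holds. As written, Section 3.1.5 misclassifies a related Grade ≥3 clinical liver event that meets no laboratory criterion, and the replacement and evaluability rules can then remove the patient from the MTD determination. The average effect is small: with replacement at a true DLT rate of 0.33, the probability of calling the dose tolerated rises by 0.0001 to 0.027 for h between 0.01% and 2%. That range is an assumption. The replacement figures treat every affected patient as replaced; keeping them as non-DLTs gives slightly larger shifts. The documents show no case that was or would have been missed, and no stated figure or sample size is wrong.

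**What to change.** Extend the hepatic item in Section 3.1.5 with: *or any treatment-related Grade ≥3 clinical hepatic event (e.g., hepatic failure, hepatic encephalopathy) regardless of laboratory values*. Keep the laboratory thresholds and the baseline-metastasis exception. Leave the words that exclude hepatic toxicity in the general item: deleting them would bring laboratory elevations under that item and override the exception.

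Then use the adverse-event and dose-interruption outputs already planned in Section 8.2.4 to check whether any Cycle 1 event of this kind went unscored or led to a replacement. With the study report already written, this check is the more useful step, and it needs no new listing.

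The cost is one phrase, with the ethics-committee or IRB approval that Section 13 requires for a protocol modification, and one look at existing outputs. The downside is a rare additional DLT, which would be clinically appropriate.
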